3.2 DLT Definition

A DLT will be defined as the occurrence of any toxicities in Table 2 occurring up to and including Day 28 of Cycle 1, except those with a clear alternative explanation (e.g., disease progression) or transient (≤ 72 hours) abnormal laboratory values without associated clinically significant signs or symptoms based on investigator and sponsor determination. All DLTs will be assessed by the investigator using CTCAE v5 criteria (NCI 2018). In order to be included in the tolerability review, subjects must have received the cohort-specific dose of itacitinib and everolimus for at least 75% of the days during the 28-day surveillance period of Cycle 1 or have experienced a DLT.

Individual subject dose reductions may be made based on events observed at any time during treatment with study drug (see Section 5.6); however, for the purposes of dose cohort escalation/de-escalation, expanding a dose cohort, and determining the RP2D, decisions will be made based on events that are observed from the first day of study drug administration through and including Day 28. A lower RP2D may subsequently be determined based on relevant toxicities that become evident after Day 28.

Subjects who experience a DLT or an unacceptable toxicity (i.e. not able to resume therapy within 28 days due to unresolved toxicity) beyond the DLT window will be also considered in the determination of the RP2D dose.

Any grade 5 hematologic and non-hematologic event related to the study treatments (at any time) will be considered a DLT.

Table 2: DLT defining toxicities

TOXICITY

Non-hematologic

- Any \geq Grade 3 non-hematologic toxicity, EXCEPT the following:
 - Transient (≤ 72 hours) abnormal laboratory values without associated clinically significant signs or symptoms.
 - Nausea, vomiting, and diarrhea adequately controlled with medical therapy within 48 hours.

Itacitinib + everolimus in HL
Version 11.0
Page 28 of 72

 Singular or non-fasting elevations in blood glucose (i.e., blood glucose excursions will be considered toxicities if fasting blood glucose is elevated on 2 separate sequential occasions).

Hematologic

- Grade 3 thrombocytopenia with bleeding.
- Grade 4 thrombocytopenia.
- Febrile neutropenia (ANC $< 1.0 \times 10^9$ /L and fever $> 101^\circ F/38.5^\circ C$).
- Grade 4 neutropenia that does not recover to \leq Grade 2 in \leq 3 days after interrupting study drug.
- Grade 4 anemia unresponsive to treatment for 3 days

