Note: itacitinib is suspected to cause transient decreases in ANC as a result of margination; therefore, DLT rules require neutropenia to persist after holding itacitinib for 3 days. The use of growth factors is permitted at the discretion of the investigator. If the clinical status of the subject allows, investigators are encouraged to wait 24 hours before starting growth factors, to determine if WBC margination is contributing to the degree of neutropenia.

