6.4.5 Cycles 2-24 Day 1 (+/- 7 days)

- Physical Examination and evaluation of ECOG PS (Appendix 13.3)
- Vital signs: blood pressure, heart rate, temperature, weight, and oxygen saturation
- CBC with differential and platelets (does not need to be repeated if previously performed within 24 hours before Day 1 Visit)
- Serum Chemistry panel including sodium, potassium, chloride, CO₂, calcium, serum creatinine, BUN, total bilirubin, alkaline phosphatase, AST, ALT, uric acid, LDH, and erythrocyte sedimentation rate (does not need to be repeated if previously performed 24 hours before Day 1 Visit)
- Review of interim adverse events and concomitant medications
- Fasting lipid profile every 2 months during active therapy (triglycerides, total cholesterol, HDL and LDL) starting with Day 1 of Cycle 2.
- QOL FACT-lym questionnaire (Appendix 13.1)

Version 11.0 Page 46 of 72

Note: Only CBC and CMP results must be received before the subject can proceed with mediation treatment. Other test results may be received after the subject has received mediation treatment.

Additional cycles of investigational treatment may be added if in the opinion of the investigator that the benefit risk ratio for the subject continues to be favorable. During these additional cycles, the same assessments will be captured as cycles 4-24.

In the event that a telemedicine visit is conducted, the following tests will be postponed until the next in-person visit:

- Physical examination
- Vital Signs
- Return of IP
- Fact-lym QOL questionnaire

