Clinical Laboratory Evaluation ^{a,b, i, m,}	X	X ⁿ	X ^g	X ^g	Xg	$X^{h, n, q}$	X	X ^f	
Antiviral Medication ^o	X								
Cohort Assignment (Phase I)		X							
Dispense Investigational Product		X				Xr			
Everolimus Availability by Subject	X								
Adverse Event Assessment			X	X		X	X		
Assess drug compliance/subject's study calendar			X	X		X	X		
Imaging ^d	X					Xq	X	Xe	
Follow-up anti-cancer treatments									X

Hematology parameters will include a complete blood count: white blood cells, red blood cells, hemoglobin, hematocrit, platelets, neutrophils, lymphocytes, monocytes, eosinophils, basophils and bands (if reported).

Version 11.0 Page 52 of 72

- Serum chemistry parameters will include sodium, potassium, chloride, blood urea nitrogen (BUN), creatinine, glucose, calcium, total protein, albumin, AST, ALT, alkaline phosphatase, total bilirubin, uric acid, LDH, erythrocyte sedimentation rate, and fasting lipid panel. Uric acid and LDH shall be performed during Screening, Cycle 1 Day 1, Cycle 1 Day 8, Day 1 of Cycle 2 through Cycle 24, and EOT. Erythrocyte sedimentation rate shall be performed during Screening, Day 1 of Cycle 1, Day 1 of Cycle 2 through Cycle 24, and EOT. The fasting lipid panel will be drawn only on screening and Day 1 of every 2 cycles (starting with Day 1 Cycle 2).
- A serum pregnancy test will be performed at screening and EOT. Urine pregnancy test will be performed only if pregnancy is suspected during treatment; positive results must be confirmed with a serum pregnancy test. Pregnancy testing will only be required for women of childbearing potential.
- Baseline imaging (preferably with FDG-PET/CT, but CT C/A/P or MRI C/A/P are also acceptable) within 8 weeks of starting therapy. If imaging was performed as standard of care before signing of the ICF but within 8 weeks of Day 1 Cycle 1, then the results from that assessment may be recorded in the eCRF in lieu of a study-specific assessment. Response assessment with imaging (investigator choice depending on clinical situation) at week 8 and 16 during the first 4 months of active therapy and every 16 weeks for the remaining active treatment period. Timing of each imaging is acceptable within +/- 1 week of the protocol specified during first 4 months of therapy and +/- 2 weeks during the remaining active treatment period.
- ^c Imaging will be performed at least every 6 months during the 2 year follow-up period after EOT and then at the discretion of the treating physician.

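### Growth factor allowed inside the 3-day recovery window can turn Grade 4 neutropenia into no DLT, and Cycle 1 schedules no fasting lipid or fasting glucose test for the Day 28 decision

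*Combined protocol and SAP*

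**What the plan says.** **Neutropenia.** Table 2 in Section 3.2 makes Grade 4 neutropenia a DLT when it fails to return to Grade 2 or better within 3 "days after interrupting study drug". The note below the table explains that itacitinib is suspected of lowering the count transiently by margination, and for this reason continues: "DLT rules require neutropenia to persist after holding itacitinib for 3 days. The use of growth factors is permitted at the discretion of the investigator". The only timing guidance is that, if clinical status allows, "investigators are encouraged to wait 24 hours before starting growth factors". Section 1.4.1.1 reports that in healthy subjects the neutrophil fall generally resolved 24 to 48 hours after stopping.

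**Glucose.** Table 2 exempts single or non-fasting elevations: "blood glucose excursions will be considered toxicities if fasting blood glucose is elevated on 2 separate sequential occasions". The Table 9 chemistry footnote lists glucose. The Cycle 1 visit lists in Sections 6.4.1 to 6.4.4 do not, and none of them calls for a fasting draw.

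**Lipids.** Grade 3 or higher non-hematologic toxicity is a DLT, subject to an exemption for laboratory values lasting at most 72 hours without signs or symptoms. Section 5.6.2.2 names hyperlipidemia as an everolimus effect and requires fasting samples to monitor it. The Table 9 footnote says "The fasting lipid panel will be drawn only on screening and Day 1 of every 2 cycles (starting with Day 1 Cycle 2"; Section 6.4.5 agrees: "Fasting lipid profile every 2 months during active therapy (triglycerides, total cholesterol, HDL and LDL) starting with Day 1 of Cycle 2". That visit has a window of 7 days either side.

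**Use of the count.** Section 3.2 bases cohort decisions on events through Day 28. It adds that later DLTs, or toxicity that prevents restart within 28 days, are also considered for the RP2D. The toxicity stopping rule in Section 7.2.2 refers to the Section 3.2 DLT. Section 8.7 gives the same boundaries but counts DLT-type events at any point.

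**The concern.** The 3-day condition has one stated job: to separate a marginated count from a truly low one. It can do that only if nothing else raises the count during those 3 days. Growth factor does raise it, so recovery after growth factor says nothing about margination, yet Table 2 scores it in the same way.

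The laboratory limb is a mismatch between what Table 2 needs and what Cycle 1 measures. Whether a given lipid or glucose abnormality becomes a DLT depends on a visit date or on an unscheduled repeat, not on the drugs.

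Establishing DLTs through Day 28 and the RP2D is the Phase I primary objective (Section 2.1.1), and the same count feeds the Phase II stopping rule. Cohorts hold 3 to 6 subjects, so one event decides the action. In Cohort 1 of Table 1, 0/3 escalates and 1/3 expands; after expansion, one further DLT de-escalates and none starts Phase II. The error runs mainly towards fewer DLTs.

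**Working it through.** **The plan's own figure.** With a Beta(1,5) prior, the posterior after x DLTs in n subjects is Beta(1 + x, 5 + n − x). The probability that the rate exceeds 30% is 78.97% at 4/6, 78.05% at 5/9, 77.52% at 6/12 and 77.23% at 7/15. Sections 7.2.2 and 8.7 state 79%, 78%, 78% and 77%. The arithmetic is right; the issue is the count that goes into it.

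**Neutropenia window.** 3 days = 72 hours. After the encouraged 24-hour wait, 72 − 24 = 48 hours remain in which growth factor can act. The wait is advisory, and 24 hours is only the lower end of the 24 to 48 hours that Section 1.4.1.1 reports for recovery.

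**Do later clauses catch an assisted recovery?** Take a subject whose Grade 4 count recovers after growth factor by hour 72 and who resumes treatment on time.
- Section 3.2, toxicity becoming evident after Day 28: no, it was evident earlier.
- Section 3.2, DLT or unacceptable toxicity beyond the window: no, it is not a DLT and treatment resumed within 28 days.
- Section 8.7, DLT-type event at any point, or no restart within 28 days: no, for the same reasons.
- Section 3.2, febrile neutropenia: counts only if fever is present.

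**Lipid date.** Cycle 2 Day 1 is nominally Day 29, and 29 ± 7 gives Day 22 to Day 36. A draw on Day 22 to 28 is inside the window; one on Day 29 to 36 is outside it.

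**Fasting draws on treatment by Day 28.** There are none on nominal timing, and at most one if the Cycle 2 visit is early. The glucose criterion needs two, so scheduled draws alone cannot meet it.

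**Illustration of size.** The missed share m is an assumption; the documents give none. With a true DLT rate of 30%, the observed rate is p = 0.30 × (1 − m). Three measures follow:
- 3+3 pass (0/3, or 1/3 then 0/3): (1 − p)³ + 3p(1 − p)⁵
- At most 1 DLT in 6, because the plan requires 6 subjects at the RP2D: (1 − p)⁶ + 6p(1 − p)⁵
- Exact probability that the stopping rule triggers at one of its looks (6, 9, 12, 15 subjects)

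| Missed share m | p | 3+3 pass | At most 1/6 | Rule stops by 15 |
|---|---|---|---|---|
| 0 | 0.300 | 49.4% | 42.0% | 19.2% |
| 10% | 0.270 | 55.7% | 48.7% | 13.1% |
| 25% | 0.225 | 65.4% | 59.4% | 6.5% |
| 50% | 0.150 | 81.4% | 77.6% | 1.2% |

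For m = 0: 0.343 + 3 × 0.3 × 0.16807 = 0.494.

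**The case against.** Several points on the other side stand.

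- **Late events are not lost.** A Grade 3 lipid result on Day 29 to 36 may still lower the RP2D under Section 3.2, and it counts under Section 8.7. It does not clearly count under Section 7.2.2.
- **A reader might infer that lipids are never measured by Day 28.** The documents do not support that, because an early Cycle 2 visit falls inside the window. A single panel also cannot show that a value lasted more than 72 hours, so adding one panel would not settle the matter.
- **A reader might infer that a glucose DLT cannot be found.** Glucose is in the Table 9 panel, Section 6.8 allows unscheduled visits at any time, and Section 8.1 contemplates repeat tests. A fasting confirmation is possible; it is just not scheduled.
- **A reader might infer that growth factor hides all serious neutropenia.** Febrile neutropenia is a DLT whatever the recovery. The recovered Grade 4 event is also still reported as an adverse event, and the Phase I primary endpoint (Sections 3.3.1.1 and 7.4) is worded as adverse events generally.
- **A reader might put a firm number on the loss.** Nothing in the documents supports one. In the everolimus cHL study described in Section 1.4.2, Grade 3 or 4 neutropenia was 5% and thrombocytopenia 32%, and none of the three gaps affects thrombocytopenia DLTs. That study did not include itacitinib, whose main drug effect in Section 1.4.1.1 is a neutrophil fall, so it does not bound the share either.

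Permitting growth factor is a matter for the investigator and is not criticised here. What none of these points answers is how an assisted recovery within 3 days is to be classified.

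**Conclusion.** The point holds in a limited form. The growth-factor gap is the firmer part. Table 2 and its note work against each other, an assisted recovery is scored as no DLT, and no other clause recovers it when fever is absent and treatment resumes on time. The laboratory part is a real but partial mismatch. Cycle 1 requires no fasting lipid or fasting glucose test, a lipid result's place in the Day 28 decision depends on the visit date, and the visit lists disagree with the Table 9 footnote on glucose.

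The true size is unknown. The table above shows sensitivity only. It assumes a true rate at the plan's 30% limit, independent subjects and a constant missed share. Requiring at most 1/6 at the RP2D lowers the levels but leaves the direction unchanged. The point should be dealt with because one event changes a cohort decision and the correction is cheap.

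**What to change.** Treat this as endpoint ascertainment and leave the management of neutropenia to the investigator.

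1. Reconcile Table 2 with its note, so that recovery after growth factor is not taken as evidence of margination when the DLT is scored. Check the general 72-hour laboratory exemption at the head of Section 3.2 at the same time, since it could exempt the same event.
2. Reconcile Table 2 with Sections 6.4.1 to 6.4.5 and the Table 9 footnote. Fasting glucose and lipids should be measured in the form Table 2 needs, on draws already scheduled within the Day 28 window, with a repeat where persistence beyond 72 hours decides the classification. List glucose consistently.
3. State how Cycle 2 Day 1 laboratory results are assigned relative to Day 28, given that the visit may fall on either side of it.
4. Reconcile Section 7.2.2 with Section 8.7, so that one definition of a countable event drives the stopping rule.

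The cost is wording, fasting instructions, a small added laboratory test, and slightly more events counted as DLTs.

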3.3 Primary Study Endpoints

AEs will be assessed using NCI CTCAE v5.0. Efficacy endpoints will be assessed using the Lugano Classification (Appendix 13.4) (19). Duration of response will be defined as the time from earliest date of disease response until earliest date of disease progression. QOL assessment will be performed by Fact-lym questionnaires (See Appendix 13.1). The presence or absence of B symptoms (fevers over 100.4°F, drenching night sweats, weight loss of 10% of baseline weight) and of pruritus will be assessed by the research staff and recorded during study visits.

3.3.1 Phase I

3.3.1.1 Primary Phase I Endpoints

Safety and tolerability will be assessed by evaluating the frequency, duration, and severity of AEs (including SAEs and dose-limiting toxicities [DLTs]) and changes in clinical and laboratory assessments.

3.3.1.2 Secondary Phase I Endpoints

Efficacy will be assessed by CR rate, ORR (CR and PR), clinical benefit (CR, PR and SD), and duration of response.

3.3.1.3 Exploratory Phase I Endpoints

- QOL (Fact-lym) questionnaires.
- B symptom and pruritus resolution.

Version 11.0 Page 29 of 72

3.3.2 Phase II

3.3.2.1 Primary Phase II Endpoints

• Efficacy will be assessed by CR rate, defined as the percentage of subjects achieving CR as their best response.

3.3.2.2 Secondary Phase II Endpoints

- ORR (CR and PR), clinical benefit (CR, PR and SD), and duration of response (defined as the time from earliest date of disease response until earliest date of disease progression).
- Safety and tolerability will be assessed by evaluating the frequency, duration, and severity of AEs (including SAEs and dose-limiting toxicities [DLTs]) and changes in clinical and laboratory assessments.

3.3.2.3 Exploratory Phase II Endpoints

- QOL (Fact-lym) questionnaires.
- B symptom and pruritus resolution.

4 STUDY POPULATION AND DURATION OF PARTICIPATION

4.1 Inclusion Criteria

- 1. Able to understand and voluntarily sign the informed consent form.
- 2. Aged 18 years or older at the time of signing the informed consent form.
- 3. Biopsy-proven diagnosis of relapsed classical Hodgkin lymphoma.
- 4. Measurable disease on imaging defined as at least one lesion that can be accurately measured in at least two dimensions by imaging (PET/CT, CT or MRI). Minimum measurement must be ≥ 15mm in the longest axis or ≥ 10mm in the short axis.
- 5. Relapsed or refractory disease (after at least 2 prior systemic therapies); patients must have relapsed after high-dose therapy with ASCT, or have been deemed ineligible for high-dose therapy with ASCT based upon the below criteria:
 - Patients that have either progressed after treatment with, be intolerant to, or are not a candidate for brentuximab and pembrolizumab or nivolumab. The reason for forgoing such therapies must be clearly documented.
 - Are not ASCT candidates due to chemo-resistant disease (unable to achieve CR or PR to salvage chemotherapy), advanced age (≥ 65 years of age), or any significant coexisting

Page 30 of 72

- medical condition (renal, pulmonary, or hepatic dysfunction) likely to have a negative impact on tolerability of ASCT
- 6. Disease free of other malignancies for greater than or equal to 2 years with the exception of basal cell, squamous cell carcinomas of the skin, fully excised melanoma in situ, carcinoma in situ of the cervix or breast.
- 7. Performance status of ECOG 0-2 (Appendix 13.3).
- 8. Laboratory test results within these ranges (of note, patients who have cytopenias due to documented cHL involvement of the bone marrow may be considered for enrollment after discussion with the PI, Medical Director and Sponsor):
 - Absolute neutrophil count (ANC) > 1,000/μL
 - Platelet count $> 75,000/\mu L$
 - Serum creatinine < 2.0 mg/dL
 - Bilirubin $< 2.0 \times ULN$ unless bilirubin increase was due to Gilbert's disease. Further evaluation should be performed to confirm and document the origin of increase.
 - AST and ALT $\leq 2.5 \times \text{institutional upper limit of normal (ULN)}$
 - Fasting cholesterol ≤ 300 mg/dL AND fasting triglycerides ≤ 300 mg/dL. NOTE: In case one or both of these thresholds are exceeded, the patient can only be included after initiation of appropriate lipid lowering medication prior initiating study treatment.
- 9. Females of childbearing potential must have a negative serum or urine beta human chorionic gonadotropin (β-hCG) pregnancy test result within 72 hours prior to the first dose of itacitinib and must agree to use an effective contraception method during the study and for 6 months following the last dose of study drug; females of non-childbearing potential are those who are post-menopausal for more than 1 year or who have had a bilateral tubal ligation or hysterectomy. Female patients undergoing active fertility preservation therapy/egg harvesting which include hCG injections are expected to have mild elevation of hCG. These patients may be allowed to participate in the trial despite elevation of hCG after providing documentation of negative hCG prior the hCG injection and statement from her fertility specialist that they are not pregnant.
- 10. Males who have partners of childbearing potential must agree to use an effective contraceptive method during the study and for 6 months following the last dose of study drug.
- 11. Must be able to comply with the study and follow-up requirements.
- 12. Subject must have access to everolimus via insurance or self-pay.

Version 11.0 Page 31 of 72

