6.7 Radiographic Evaluations

Subjects will undergo radiographic evaluations to assess disease status at the time points listed below. Timing of radiographic evaluations may be altered based on clinical indication or the discretion of the treating physician.

- Baseline imaging (preferably with FDG-PET/CT, but CT C/A/P or MRI C/A/P are also acceptable) within 8 weeks of starting therapy.
- If imaging was performed as standard of care before signing of the ICF but within 8 weeks of Day 1, then the results from that assessment may be recorded in the eCRF in lieu of a study-specific assessment.
- Response assessment with imaging (investigator choice depending on clinical situation) at week 8 and 16 during the first 4 months of active therapy and every 16 weeks for the remaining active treatment period.
- Imaging will be performed at least every 6 months during the 2 year follow-up period after EOT for patients who came off study for reasons other than progression and who did not start another therapy.

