13.4 Revised Criteria for Response Assessment of Malignant Lymphoma[19]

The following table provides a summary of response criteria for malignant lymphoma according to Cheson (2014). Please refer to published international guidelines for the most recent and complete details.

Site	PET-Based Response	CT-Based Response
	Complete metabolic response	Complete radiologic response (all of the following)
Lymph nodes and extralymphatic sites	Score 1, 2, or 3 with or without a residual mass on 5PS. ^a	Target nodes/nodal masses must regress to ≤ 1.5 cm in LDi.
Nonmeasured lesion	Not applicable.	Absent.
Organ enlargement	Not applicable.	Regress to normal.
New lesions	None.	None.
Bone marrow	No evidence of FDG-avid disease in marrow.	Normal by morphology; if indeterminate, IHC negative.
	Partial metabolic response	Partial remission (all of the following)
Lymph nodes and extralymphatic sites	 Score 4 or 5a with reduced uptake compared with baseline and residual mass(es) of any size. At interim, these findings suggest responding disease. At EOT, these findings suggest residual disease. 	 ≥ 50% decrease in SPD of up to 6 target measurable nodes and extranodal sites. When a lesion is too small to measure on CT, assign 5 mm × 5 mm as the default. When no longer visible, 0 × 0 mm. For a node > 5 mm × 5 mm but smaller than normal, use actual measurement.
Nonmeasured lesions	Not applicable.	Absent/regressed, but no increase.
Organ enlargement	Not applicable.	Spleen must have regressed by > 50% in length beyond normal.
New lesions	None.	None.
Bone marrow	Residual uptake higher than uptake in normal marrow but reduced compared with baseline (diffuse uptake compatible with reactive changes from chemotherapy allowed). If there are persistent focal changes in the marrow in the context of a nodal response, consider further evaluation with MRI or biopsy.	Not applicable.
Lymph nodes and extralymphatic sites	 Score 4 or 5a with reduced uptake compared with baseline and residual mass(es) of any size. At interim, these findings suggest responding disease. At EOT, these findings suggest residual disease. 	 ≥ 50% decrease in SPD of up to 6 target measurable nodes and extranodal sites. When a lesion is too small to measure on CT, assign 5 mm × 5 mm as the default. When no longer visible, 0 × 0 mm. For a node > 5 mm × 5 mm but smaller than normal, use actual measurement.

Page 71 of 72

Site	PET-Based Response	CT-Based Response	

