LDi = longest transverse diameter of lesion; PPD = cross product of the LDi and perpendicular diameter; SDi = shortest axis perpendicular to the LDi; SPD = sum of the product of the perpendicular diameters for multiple lesions.

a PET 5-point scale: 1) no uptake above background; 2) update ≤ mediastinum; 3) uptake > mediastinum but ≤ liver;
4) uptake moderately > liver; 5) uptake markedly higher than liver and/or new lesions; X) new areas of uptake unlikely to be related to lymphoma.

Itacitinib + everolimus in HL
Version 11.0
Page 72 of 72

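### Inclusion item 4 admits nodes already within the CT size limit for complete response, so a subject with only small nodes and no PET could be scored CR on a change within measurement error

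*Combined protocol and SAP*

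**What the plan says.** **Entry.** Section 4.1, item 4 asks for at least one lesion measurable in two dimensions on PET/CT, CT or MRI, and adds: "Minimum measurement must be ≥ 15mm in the longest axis or ≥ 10mm in the short axis".

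**CT-based CR.** The CT column of Appendix 13.4 states: "Target nodes/nodal masses must regress to ≤ 1.5 cm in LDi". The footnote defines the term: "LDi = longest transverse diameter of lesion". The other conditions in that column must hold too: nonmeasured lesions gone, organs back to normal size, no new lesions, marrow normal.

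**PET-based CR.** The PET column does not depend on size: "Score 1, 2, or 3 with or without a residual mass on 5PS".

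**Modality.** Section 6.7 describes baseline imaging as "preferably with FDG-PET/CT, but CT C/A/P or MRI C/A/P are also acceptable". For response it says: "Response assessment with imaging (investigator choice depending on clinical situation) at week 8 and 16". The imaging footnote to Table 9 repeats both.

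**Endpoint.** Sections 3.3.2.1 and 7.4 count any subject whose best overall response is CR under the Lugano Classification. Section 7.1 sets a null CR rate of 5%, an alternative of 25% and 17 subjects. The study stops if none of the first 9 evaluable subjects has a CR.

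**The concern.** The entry criterion and the response criterion share the 15 mm boundary, and the short-axis alternative reaches below it. A subject can enter with disease that is already small enough for CT-based nodal CR. The size criterion then does little to separate a true response from variation between two readings.

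This matters because so few events decide the trial. Stage 1 turns on whether there is any CR in 9 subjects, and final success turns on 2 or 3 CRs. A single misclassified subject can carry the study past the futility look and bring it close to the success threshold. The 5% null rate rests on experience with everolimus alone, so a CR produced by the size rule would be read as benefit of the combination.

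**Working it through.** **1. The two thresholds side by side**

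| Baseline node | Qualifies under item 4? | Longest diameter already at most 15 mm? |
|---|---|---|
| 12 x 10 mm | Yes, by short axis | Yes |
| 15 mm longest axis | Yes, by longest axis | Yes |
| 16 x 9 mm | Yes, by longest axis | No |

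The overlap is every node with short axis at least 10 mm and longest diameter at most 15 mm, plus any node of exactly 15 mm. The progression criteria in Appendix 13.4 treat a node as abnormal only above 1.5 cm, and count a new node only above 1.5 cm. Item 4 therefore admits, as sole measurable disease, nodes no larger than the appendix's own cut-off. Sections 4.1, 6.7 and 7.4 and Appendix 13.4 set no minimum baseline diameter for a target node, no minimum shrinkage for CT-based CR and no PET confirmation.

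**2. The plan's design reproduced**

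Inputs: null 5%, alternative 25%, one-sided alpha 0.05, power 80% (section 7.1). An exact search for the Simon optimal design returns 9 in stage 1, stop at 0 CR, total 17, success at 3 or more CRs. Alpha is 0.0466 and power 0.812, so the stated 9 and 17 reproduce.

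With X the CRs among the first 9 and p = 0.05:

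- P(X = 0) = 0.95^9 = 0.630, the chance of a futility stop.
- P(X = 1) = 9 x 0.05 x 0.95^8 = 0.2985; P(X = 2) = 0.0629; P(X ≥ 3) = 0.0084.
- Among the next 8: P(≥ 1) = 0.3366; P(≥ 2) = 0.0572.
- False success = 0.2985 x 0.0572 + 0.0629 x 0.3366 + 0.0084 = 0.047.

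**3. One affected subject (assumed), scored CR; the other 16 at 5%**

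- Among the first 9: the stop cannot occur, and at least 2 CRs are needed from 16. That is 1 - 0.95^16 - 16 x 0.05 x 0.95^15 = 1 - 0.440 - 0.371 = 0.189.
- Among the last 8: stage 1 must pass without this subject. That is P(X = 1) x (1 - 0.95^7) + P(X ≥ 2) = 0.2985 x 0.3017 + 0.0712 = 0.161.

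**4. Range, because the frequency is not in the documents**

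| Assumption (success at 3 or more CRs) | False-success probability |
|---|---|
| No affected subject | 0.047 |
| One, in the last 8 | 0.161 |
| One, in the first 9 | 0.189 |
| Two, in the first 9 (1 - 0.95^15) | 0.537 |
| Each subject affected with probability 5% (rate 0.05 + 0.95 x 0.05 = 0.0975) | 0.212 |
| Same, 10% (rate 0.145) | 0.433 |

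Every row takes each affected subject as scored CR, so these are upper values for the assumed number or share.

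**5. The written success rule**

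Section 7.4 declares success at 2 or more CRs. With 9/17 that gives 0.2985 x 0.3366 + 0.0712 = 0.172 with nobody affected, 1 - 0.95^16 = 0.560 with one affected in the first 9, and 1 - 0.630 = 0.370 with one in the last 8. The starting value of 0.172 comes from a separate error: 2 is below the 3 that the design requires. These figures therefore mix two problems, and I do not use them to size this one.

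**The case against.** The case on the other side is substantial.

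- **No change is not CR.** Appendix 13.4 requires nodes to regress to the limit. A reader might infer that a subject with a small node becomes CR automatically, with no change at all. The wording does not support that, because an unchanged node has not regressed. What stands is that no amount of regression is set, so 1 or 2 mm would satisfy it. The documents give no measurement-error figure; 1-2 mm is my illustration.
- **The other CT conditions apply.** Every target node must meet the limit, and nonmeasured disease must be absent. Exposure is confined to subjects whose whole disease is small-volume nodal. After at least two prior systemic therapies, such subjects are likely to be rare. This narrows the gap without closing it, since one lesion suffices for entry. The marrow condition adds little, because neither section 6.1 nor Table 9 schedules a marrow examination.
- **PET will often be used.** It is preferred at baseline, and PET-based CR ignores size. But it is optional at baseline, and the response modality is the investigator's choice.
- **The appendix is a summary.** It refers to the published guidelines for full detail and does not say how target nodes are chosen. If a 12 x 10 mm node could not be a target, it might count as a nonmeasured lesion that must disappear. The documents do not settle this, which is itself a reason to write the rule down.

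**Conclusion.** The concern holds in a narrow form. Item 4 accepts, as sole measurable disease, nodes already within the CT size limit for CR. With no mandatory PET and no minimum shrinkage, a subject with only small-volume nodal disease, no nonmeasured disease and CT or MRI assessment alone could be scored CR after a change within measurement error.

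The size is conditional. If one such subject occurs among 17 and is scored CR, false success at a true CR rate of 5% rises from 4.7% to 16-19% under the 9/17 design with 3 or more CRs. If that subject is among the first 9, the futility stop is lost. A reader might infer that the trial's error rate actually is 16-19%, or 37-56% under the written rule. The documents do not support either reading: they give no frequency of affected subjects, and the second range also carries the separate error in the success threshold.

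**What to change.** **Section 4.1, item 4, for new subjects.** Require a longest diameter above 15 mm for a qualifying nodal lesion, and state a separate size limit for extranodal lesions. Item 4 speaks of lesions, not only nodes, and the CT limit in Appendix 13.4 is worded for nodes.

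**Section 7.4 and Appendix 13.4.** State that nodes with a baseline longest diameter of 1.5 cm or less cannot by themselves support a CT-based CR. A subject whose only measurable disease is such nodes can be CR only by PET, with a 5-point score of 1 to 3. Subjects with extranodal disease remain assessable for CR by CT on resolution of that disease. This also covers subjects already enrolled.

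**Cost.** Wording only: no added subjects, and no visits beyond a PET where such a subject is to be eligible for CR. The downside is that a rare subject with only small nodes and no PET cannot be counted as CR. One limit remains: a 16 mm node that shrinks to 15 mm still meets the CT size criterion. The change removes the overlap at entry but does not introduce a minimum shrinkage.
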